## Abbreviations

AIFA	Agenzia Italiana del Farmaco
ARDS	Acute Respiratory Distress Syndrome
BMI	Body Mass Index
COVID-19	Coronavirus Disease 19
CTA	Clinical Trial Authorization
DM	Dexamethasone
DSMB	Data safety and monitoring board
ECMO	Extracorporeal Membrane Oxygenation
HFNC	High-Flow nasal cannula
GC	Glucocorticoid
GR $\alpha$	Glucocorticoid Receptor alpha
ICU	Intensive care unit
IV	Intravenously
LMWH	Low molecular weight heparin
IMV	Invasive mechanical ventilation
MP	Methylprednisolone
MV	Mechanical ventilation (both NPPV and IMV)
NOAC	New oral anticoagulants
NPPV	Noninvasive positive pressure ventilation
PEEP	Positive End-Expiratory Pressure
PO	Per os
RHDU	Respiratory high-dependency unit
RT-qPCR	Real-time quantitative polymerase chain reaction
SAE	Serious adverse event
SARS-CoV-2	Severe Acute Respiratory Syndrome-Coronavirus-2
SoC	Standard of care
SUSAR	Suspected Unexpected Serious Adverse Reaction
WHO	World Health Organization

## 2. Introduction

### 2.1. Background and rationale

Severe Acute Respiratory Syndrome-Coronavirus-2 (SARS-CoV-2) infection is associated with an acute respiratory decompensation requiring supplemental oxygen therapy in approximately 60% of the hospitalized cases and with acute respiratory distress syndrome (ARDS) requiring mechanical ventilation in about 20% of cases.(1) The rationale for glucocorticoid treatment in COVID-19 was recently reviewed.(2) Low-dose glucocorticoid (GC) treatment is the only intervention shown to significantly reduce mortality in cases of COVID-19 pneumonia requiring oxygen supplementation or ventilatory support. In particular, a large UK randomized controlled trial (RECOVERY trial) demonstrated the efficacy of dexamethasone at a dosage of 6mg/day for 10 days in reducing mortality by 17% on average compared to usual therapy, with a greater impact on patients requiring mechanical ventilation (36% reduction) or oxygen therapy (18% reduction) than on those who did not need respiratory support.(1)

Several other RCTs have shown similar results, confirming the strong rationale for the use of glucocorticoids in moderate and severe SARS-CoV-2 pneumonia.(3) Nevertheless, generally speaking, there is paucity of information guiding glucocorticoid administration in severe pneumonia and ARDS, which led to a great heterogeneity of treatment protocols and misinterpretation of available findings. Glucocorticoids are a large group of agonist compounds that bind to the glucocorticoid receptor alpha (GR $\alpha$ ) producing similar pharmacological response, but their specific anti-inflammatory effect and pharmacological properties are different. Clinical efficacy depends on the magnitude and duration of exposure to GC, including genomic and non-genomic effects. The pharmacological principles guiding prolonged glucocorticoid treatment in ARDS have been recently reviewed.(4,5) Based on RCTs findings, GC plasma concentration-time profiles and pharmacodynamic studies, optimal results are most likely achievable with early intervention and an administration schedule that consists of an initial bolus dose to achieve close-to-maximal GR $\alpha$  saturation, followed by a continuous infusion to maintain high levels of response throughout the treatment period.(6) In addition, patients receiving similar GC doses may experience substantial between-patient variability in plasma concentrations affecting clinical response.(5) GC should be dose-adjusted and administered for a duration targeting clinical and laboratory improvement, followed by dose-tapering to achieve gradual recovery of the suppressed hypothalamic-pituitary-adrenal (HPA) axis. These findings have practical clinical relevance. At present, however, there is no evidence of the superiority of a steroid drug -nor of a therapeutic scheme- compared to the others, due to the lack of comparative studies.

In a recent longitudinal observational study conducted in 14 Italian RHDUs, a protocol with prolonged low-dose methylprednisolone, administered in a subgroup of patients with severe

EudraCT number: 2020-006054-43

pneumonia and high levels of systemic inflammation, demonstrated a 71% reduction in mortality and the achievement of other secondary endpoints such as an increase in ventilation-free days by study day 28.(7) The treatment was well tolerated and did not affect viral shedding from the airways.

The main differences between the protocol used in this study and that one used in the RECOVERY trial are: a) the use of a treatment protocol with a strong biochemical and pharmacological rationale, that had already proven effective in reducing mortality in severe pneumonia of both bacterial and viral etiology in previous RCTs; b) the possibility to titrate treatment duration on parameters reflecting clinical severity; c) the slow dosage de-escalation, in order to avoid inflammatory rebound. Furthermore, bioinformatics studies support the greater theoretical efficacy of methylprednisolone over dexamethasone based on their molecular targets during SARS-CoV-2 infection.(8)

In light of these data, the present study aims to compare in hospitalized patients needing noninvasive respiratory support (oxygen supplementation, HFNC, NPPV) the efficacy of methylprednisolone 80 mg in continuous IV infusion over 24 hours for at least 8 days and that of dexamethasone 6 mg IV/PO once daily for 10 days in increasing survival by day 28, as well as in reducing the need and duration for mechanical ventilation.

## 2.2. Objectives

We hypothesize that in patients hospitalized for COVID-19 pneumonia requiring respiratory support (either oxygen supplementation, HFNC, NPPV), the methylprednisolone protocol is superior to the dexamethasone protocol in improving clinical outcomes.

The primary objective is to assess the efficacy of the methylprednisolone protocol in improving survival by day 28 compared to the dexamethasone protocol.

The secondary objectives are to compare efficacy of the two protocols in achieving:

- a) Reduction in the need and duration of mechanical ventilation
- b) Reduction in hospital mortality
- c) Reduction in the duration of hospitalization
- d) Reduction in duration of requirement for oxygen supplementation

Additional end-points include anti-inflammatory potency based on longitudinal reduction in systemic C-reactive protein levels and reduction in disease progression based on the WHO clinical progression scale.(9)

## 3. Study design

This study is a phase 3 adaptive randomized controlled trial (2 parallel arms, allocation ratio 1:1) implemented during a massive epidemic emergency. Adaptation is a carefully considered

investigational procedure for modifying study parameters while the trial is ongoing, based on a review of the interim data analyses.(10–12)

Our adaptive trial is a sequential random controlled trial, with 2 interim analyses (K=3). We aim to evaluate the safety and efficacy of two different protocol of steroids therapy in adult patients with severe COVID-19.

The trial adaptive framework includes:

- a) a 3-stage sequential O'Brien and Fleming design;
- b) sample size re-calculation at each stage;
- c) binding stopping rule for efficacy according with preplanned critical values;
- d) binding stopping rule for futility according with a preplanned critical values.

### 3.1. Sequential design

Sequential design is a pivotal element of the adaptive strategy that allows for assessing participants data while the trial is ongoing for optimizing trial performance. In this study, we include a 3-stage procedure with two homogeneous interim analyses and one final analysis (K=3). Sequential design is always associated with inflation of statistical error due to multiple comparisons on the same accrued set of data. To control for this bias, we have defined ad hoc statistical plan and define adequate error spending function. When the sample size expected for each interim analysis is reached, patients will continue to be enrolled and randomized until either the results of that interim analysis will be available or the minimum sample size expected for the subsequent stage will be reached.

### 3.2. Sample size recalculation

The adequacy of sample size is important for clinical trials. However, in the current circumstance there are significant uncertainties about the sizes of parameters that are needed for optimizing study power. To prevent under-powering (i.e. leading to drop of efficacious intervention) and oversizing (leading to expanding time and cost of the study) we will implement a sequential recalculation of the sample size for each one of the three interim analyses.

### 3.3. Stopping rule for efficacy

Stopping rule for efficacy allows to early terminating the trial if a significant effect of methylprednisolone is already evident in the early analysis. Stopping rule for efficacy implies early rejection of H0 by using accruing data from ongoing trial and thus it is associated with an inflation of type I error. To prevent this issue we have defined a preplanned analysis with predefined critical value and a formal alpha spending function.

### 3.4. Stopping rule for futility

Stopping rule for futility allows to early terminating the trial if interim analysis does not support the efficacy of methylprednisolone. Stopping rule for efficacy implies early acceptance of H0 by using accruing data from ongoing trial and thus it is associated with an inflation of type II error. To prevent this issue we have defined a preplanned analysis with predefined critical value and a formal beta-spending function.

## 4. Methods: participants, interventions and outcomes

### 4.1. Study Setting

This is a multi-center study involving Italian hospitals. The study population will be drawn from any patient admitted to the participating Centers, who tested positive RT-qPCR-positive on at least one upper respiratory swab, bronchial wash or bronchoalveolar lavage. There will be no restrictions on race, gender or ethnicity. Minors (aged <18y) will be excluded in order to simplify the informed consent acquisition procedure.

### 4.2. Eligibility Criteria

Inclusion criteria are the following:

- a) Able to understand and sign the informed consent form
- b) SARS-CoV-2 positive on at least one upper respiratory swab or bronchoalveolar lavage
- c)  $\text{PaO}_2 \leq 60$  mmHg or  $\text{SpO}_2 \leq 90\%$  or on HFNC, CPAP or NPPV at randomization
- d) Age  $\geq 18$  years old at randomization

Exclusion criteria are the following:

- a) On invasive mechanical ventilation (either intubated or tracheostomized)
- b) Heart failure as the main cause of acute respiratory failure
- c) On long-term oxygen or home mechanical ventilation
- d) Decompensated liver cirrhosis
- e) Immunosuppression (i.e., cancer on treatment, post-organ transplantation, HIV-positive, on immunosuppressant therapy)
- f) On chronic steroid therapy or other immunomodulant therapy (e.g., azathioprine, methotrexate, mycophenolate, convalescent/hyperimmune plasma)
- g) Chronic renal failure with dialysis dependence
- h) Progressive neuro-muscular disorders
- i) Cognitively impaired, dementia or decompensated psychiatric disorder
- j) Quadriplegia/Hemiplegia or quadriparesis/hemiparesis
- k) Do-not-resuscitate order

- l) Participating in other clinical trial including experimental compound with proved or expected activity against SARS-CoV-2 infection
- m) Any other condition that in the opinion of the investigator may significantly impact with patient's capability to comply with protocol intervention
- n) Refuse to participate in the study or absence of signed informed consent form.

#### 4.3. Interventions

All patients who meet the above inclusion and exclusion criteria are randomized to one of the following treatment protocols.

##### 1. Arm 1 (methylprednisolone, MP):

- A. On day 1, loading dose of MP 80 mg IV in 30 minutes, promptly followed by continuous infusion of MP 80 mg/day in 240 mL of normal saline at 10 mL/h.
- B. From day 2 to day 8: infusion of MP 80 mg/day in 240 mL of normal saline at 10 mL/h.
- C. From day 9 and beyond:
  - a) If not intubated patient and  $\text{PaO}_2/\text{FiO}_2 > 200$ , taper to MP 20 mg IV in 30 minutes three times a day for 3 days, then MP 20 mg IV twice daily for 3 days, then MP 20 mg IV once daily for 2 days, then switch to MP 16 mg/day PO for 2 days, then MP 8mg/day PO for 2 days, then MP 4mg/day PO for 2 days;
  - b) If intubated patient or  $\text{PaO}_2/\text{FiO}_2 \leq 200$  with at least 5 cmH2O CPAP, continue infusion of MP 80 mg/day in 240 mL of normal saline at 10 mL/h until  $\text{PaO}_2/\text{FiO}_2 > 200$  then taper as in a)

##### 2. Arm 2 (dexamethasone, DM)

- A. DM 6 mg IV in 30 minutes or PO from day 1 to day 10 or until hospital discharge (if sooner).
- B. After day 10 study treatment is interrupted.

Both methylprednisolone and dexamethasone are licensed in Italy. They have been widely used in clinical practice for many years and have proven efficacy in a variety of syndromes including COVID-19, with limited toxicity or adverse reactions.

Both drugs will be stored and administered in accordance with standard pharmacy procedures; they are both routinely available on the hospital formulary.

Both drugs will be given open label by either intravenous injection diluted to the treating dose in the appropriate diluent or *per os* according to treatment protocol.

#### 4.4. Standard of Care (SoC)

Both groups receive the same SoC. In particular:

- Respiratory support (oxygen therapy, HFNC, NPPV, IMV, ECMO) is granted to all patients and titrated on the failure of the previous line in improving oxygenation (assessed by PaO2/FiO2 ratio) after 24-48 hours.
- Anticoagulation with low molecular weight or unfractionated heparin must be always administered, at either prophylactic or anticoagulant dose according to clinical need (eg, conditions that require guidelines-directed anticoagulation) or pre-existing comorbidities (eg, already on anticoagulants).

Additional therapies are allowed but they must be specified in the appropriate section of the data collection form.

#### 4.5. Outcomes

##### Primary outcome measure

- Survival proportion at 28 days in both arms

##### Secondary outcome measures

- Number of days free from mechanical ventilation (either NPPV or IMV) by study day 28 in both arms
- Number of days of hospitalization among survivors in both arms
- Proportion of patients requiring tracheostomy in both arms
- C-reactive protein level (mg/L) at study day 3, 7 and 14 in both arms
- PaO2/FiO2 ratio (mmHg) at study day 3, 7 and 14 in both arms
- WHO clinical progression scale at study day 3, 7 and 14 in both arms(9)

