## 6. Statistical plan

### 6.1. Sequential design procedures

This is a sequential open label randomized clinical trial with 2 interim analyses ( $K=3$ ) with unblinded sample size recalculation (adaptive sample size), stopping rule for early efficacy and stopping rule for futility according to O'Brien and Fleming sequential study design. Stopping rule for either futility or efficacy are bound to specific error spending function according to a Fisher's exact test calculated on primary outcome.

The experimental hypothesis of the study is that treatment with MP improves 28-day survival from 77% in arm 2 to 87% in arm 1 (i.e. risk difference 10%). If this hypothesis is true, the study has a one tail alpha-error  $<0.025$  and an overall power  $>90\%$  by using a Fisher's exact test and critical alpha and beta error value for type I and type II error spending function.

Preplanned critical values and plots are reported in table 1 and figure 1, respectively.

[figure not shown]

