## 6.2. Sample size

Minimum and maximum sample size will significantly change according to the observed effect within the trial sample (expected **average** sample size is between 200 and 680 participants, figure 2). In particular, we expect to enroll 100 participants per arm at the first stage and then between 15 and 175 per arm for each eventual stage if the stopping rules were not met. The actual number of new participants in each arm will be calculated according to the maximum likelihood estimates on observed efficacy at each interim analysis with an overall conditional power for next stage equal to 90%. This approach allows either to minimize the number of enrolled participants if the experimental hypothesis is too conservative or to have a good power level if the experimental hypothesis is too optimistic. The average sample size with relative power and the overall probability for meeting stopping rules according to different level of efficacy of arm 1 vs. arm 2 are reported in figure 2 and figure 3, respectively.

	$H_0: \pi_T - \pi_C = 0$			
Critical values	Stage 1	Stage 2	Stage 3	
Reject H0 (Efficacy)	3.421	2.419	1.975	1.975
Accept H0 (Futility)	-0.695	1.002	1.975	1.975
Information rate	0.333	0.667	1	1
alpha spent	0.0003	0.0079	0.025	0.025

*Table 1 Preplanned critical values (Fisher test) for application of early stopping rules*

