**K = 3; alpha = 0.025, one-sided, binding futility = (-0.695, 1.002), Delta = 0 (O'Brien and Fleming design).**

Figure 1 Plot for application of early stopping rule. Uncertainty area (i.e.  $H_0$  is neither accepted nor rejected) lies above the green line and below the red lines

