#### 6.4. Analysis of secondary outcomes

Binary variables (i.e., proportion of patients requiring tracheostomy) will be modelled according to separate logistic regression models to assess the potential effect of each different treatment arm. All models will be adjusted for the effect of age and gender in the case of unbalanced groups following randomization.

[figure not shown]
Continuous variables including the number of days free from mechanical ventilation, number of days of hospitalization, C-reactive protein level (mg/L) at study day 3, 7, 14 and PaO2/FiO2 ratio (mmHg) at study day 3, 7 and 14 after randomization will be modelled by linear regression models and the estimates will be given adjusted for age and sex in the case of unbalanced groups following randomization.

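### Hospital stay is compared only among survivors although the trial expects survival to differ by arm, so this secondary comparison is not randomised and is open to selection bias

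*Protocol*

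**What the plan says.** Objective (c) in section 2.2 is "Reduction in the duration of hospitalization", with no restriction to survivors. The matching outcome in section 4.5 is narrower: "Number of days of hospitalization among survivors in both arms". It does not say whether survival is counted to day 28 or to discharge.

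Section 6.4 treats this outcome as an ordinary continuous variable, in the group "Continuous variables including the number of days free from mechanical ventilation, number of days of hospitalization". The model is linear regression, with age and sex added if randomisation leaves the groups unbalanced. Section 6.4 does not mention death.

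Section 6.1 builds the design on 28-day survival rising from 77% (dexamethasone) to 87% (methylprednisolone). Section 6.3 says that all analyses follow intention to treat. That sentence stands in the primary-outcome section but is worded generally.

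The neighbouring outcome is "Number of days free from mechanical ventilation (either NPPV or IMV) by study day 28 in both arms". It is not restricted to survivors, and no value is given for a patient who dies.

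**The concern.** Randomisation makes the two arms comparable as a whole. It does not make the survivors of one arm comparable with the survivors of the other when treatment affects who survives. Here a survival difference is the trial's own hypothesis. If it is true, the methylprednisolone survivors include patients who would have died on dexamethasone, and the dexamethasone survivors include no such group.

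If those extra survivors are sicker and stay longer, methylprednisolone would appear to lengthen stay without lengthening any patient's stay. Objective (c) could then point the wrong way in exactly the situation where the primary hypothesis is true. Adjusting for age and sex does not repair this. The imbalance comes from survival, and section 6.4 provides the adjustment only for imbalance left by randomisation.

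**Working it through.** **The plan's own figures.** The protocol states no figure for hospital stay. The figures tied to the 77% versus 87% hypothesis belong to the primary design, and they reproduce:

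- Cumulative alpha in Table 1 is 0.0003 / 0.0079 / 0.025. Numerical integration with the tabulated bounds gives 0.00031 / 0.00789 / 0.02498.
- Stated power is above 90%. A simulation of 20,000 trials gives 90.2%. It used 100 per arm at stage 1, then 15 to 175 per arm, with one-sided Fisher p-values. Inverse-normal combination of the stages is an assumption.

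None of this is affected by what follows.

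**Inputs for stay.** Survival of 77% and 87% comes from section 6.1. Survivors are taken as alive at day 28. Two assumptions are not in the documents: methylprednisolone harms no one who would survive on dexamethasone, and it does not change those patients' stay.

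**Step 1: patients without a counterpart.** Per 100 patients per arm, 77 survive on either drug and 87 − 77 = 10 survive only on methylprednisolone. Their share of methylprednisolone survivors is 10/87 = 11.5%.

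**Step 2: the artefact in mean stay.** Let the 77 stay 15 days on average (assumed) and the extra 10 stay L days (assumed). The apparent difference, methylprednisolone minus dexamethasone, is (77 × 15 + 10 × L)/87 − 15 = 10 × (L − 15)/87.

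| L (days) | Apparent difference (days) |
|---|---|
| 12 | −0.34 |
| 15 | 0 |
| 25 | +1.15 |
| 30 | +1.72 |
| 40 | +2.87 |

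Only L − 15 matters, so the 15-day base can be replaced by any other value.

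**Step 3: could it look like a finding?** Assume 300 per arm, which gives 0.87 × 300 = 261 and 0.77 × 300 = 231 survivors. The standard error is SD × √(1/261 + 1/231) = 0.0903 × SD. For an artefact of 1.15 days, the chance of a significantly longer methylprednisolone stay (z above 1.96) is 36% at SD 8, 25% at SD 10 and 18% at SD 12. The SDs are assumed.

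**Step 4: ventilation-free days under different scores for death.** If the drug only saves 10 in 100 patients, the contrast is 0.10 × (score if saved − score if dead). Five assumed patterns of ventilation and death gave:

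| Score for death | Methylprednisolone minus dexamethasone (days) |
|---|---|
| 0 | +1.4 to +1.8 |
| Days alive and off ventilation | +0.8 to +1.2 |
| 28 minus ventilation days, death ignored | −1.1 to +1.0 |

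The extremes of the last row are:

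- 3 ventilation days before death against 14 if saved: 0.10 × (14 − 25) = −1.1.
- 20 ventilation days before death against 10 if saved: 0.10 × (18 − 8) = +1.0.

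**The case against.** The strongest reply is that the direction of the bias in stay is assumed. The protocol has no length-of-stay data, the sizes in step 2 come wholly from assumed stays, and the sign reverses if the extra survivors leave sooner than the others. The restriction is also openly labelled, and survival is reported beside it as the primary outcome. All of this stands, and it limits what can be said about direction and size. It does not make the comparison a randomised one, and labelling does not bring the outcome into line with the unrestricted objective (c).

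A reader might go further and infer that both day-count outcomes are biased against methylprednisolone, with ventilation-free days shifted by about 2 days. The documents do not support this:

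- Section 4.5 gives no score for death in ventilation-free days. It does not give a wrong one, and a statistical analysis plan that is not shown may supply it.
- A figure of 2 days (0.10 × 20, for a death after 8 ventilation days scored 20 instead of 0) is the gap between two scoring rules. It leaves out the saved patient's own score. The net contrast under the least favourable rule runs from −1.1 to +1.0, and under the other two rules it favours methylprednisolone throughout.
- Ventilation-free days are not restricted to survivors, so the loss of randomised comparability applies to stay alone.

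Objecting to linear regression because the outcomes are bounded or skewed is partly a preference. The model estimates a mean difference, and the spike at 0 arises only once deaths are scored 0.

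**Conclusion.** The point holds for hospital stay. The protocol fixes a secondary comparison that conditions on survival while expecting survival to differ by 10 percentage points, and that comparison does not match objective (c) as written. If the hypothesis is true and no one is harmed, 11.5% of methylprednisolone survivors have no counterpart. The resulting bias is plausibly, but not certainly, against the arm with better survival. It is +1.1 to +2.9 days if the extra survivors stay 10 to 25 days longer than the others, and negative if they stay less; these stays are assumed.

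For ventilation-free days there is only a clarification to make, since 28 minus ventilation days would credit days after death as free days. No bias is demonstrated.

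The primary outcome, alpha and sample size are untouched. The change should be made, but the trial's main conclusion does not depend on it.

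**What to change.** - For objective (c), analyse all randomised patients by time to discharge alive, with death as a competing event. The alternative is days alive and out of hospital to day 28, with death by day 28 scored 0. Name one of these as the analysis of the objective.
- Keep stay among survivors as a descriptive line, and say whether survivors means alive at day 28 or at discharge.
- State in section 4.5 or in the analysis plan that death by day 28 scores 0 in ventilation-free days.

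The cost is wording. Section 4.6 already collects the dates of randomisation, discharge and death, and ventilation-day totals at day 28. Two limits apply. One discharge date is listed and no readmission, so days out of hospital would rest on the first discharge; time to discharge alive does not have this problem. After a switch to invasive ventilation and back, only the end of the second noninvasive session is entered, so ventilation-free days should use the collected totals and not be rebuilt from those dates.

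The drawback is small: the new measure mixes survival with duration. The descriptive survivor line offsets this.
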